#### 8.2.4 Vaccine Efficacy Accounting for Number of Founding Viruses

Another secondary analysis may be conducted to assess the vaccine efficacy on HIV-1 acquisition over 24 months using the method of [Follmann and Huang \(2015\)](#) that incorporates information on the number of HIV-1 founder viruses in HIV-1-infected participants. The method has increased efficiency relative to Cox proportional hazards regression if the vaccine reduces the number of founders.

### 8.3 Analysis of Exploratory Objective 1

The use of oral FTC/TDF as PrEP will be assessed as described in [Section 10.2](#).

### 8.4 Analysis of Exploratory Objective 2

If there is substantial PrEP use detection at baseline, then the Cox model will be used to assess whether vaccine efficacy significantly differs in subgroups with detectable versus undetectable baseline PrEP use, and to make inferences on vaccine efficacy separately in each subgroup. In addition, if there is substantial PrEP use detected over the course of the study, then a Cox model with PrEP detectability as a time-varying covariate will be used to assess different vaccine efficacy by time-varying subgroup and for each subgroup separately.

More specifically, the primary analysis will be repeated where only MITT infection endpoints with no evidence of PrEP use at the time of HIV-1 diagnosis and at the time of the earliest evidence of infection will be included in the analysis. Intracellular tenofovir (TFV) concentration (see [Section 8.3](#)) will be used to determine eligibility for this analysis. A participant is eligible if the TFV concentration is below the lower limit of detection as defined above at the diagnosis visit and at the visit with earliest evidence of HIV-1 infection (if different from the diagnosis visit). Since the ARVs are only detectable in plasma for roughly 14 days ([Patterson et al. 2010](#)) and some participants may have become infected before the 14-day window, with this approach we are not assured that all those included in the analysis were not using prophylactic ARVs at the time of infection. Therefore an additional analysis may be conducted that addresses this issue by also excluding participants from the HIV-1 acquisition analysis if they self-reported ARV use in the last 30 days at either the diagnosis

visit or the last visit prior to diagnosis. These analyses will evaluate uninfected participants without accounting for data on their TFV concentrations.

## 8.5 Analysis of Exploratory Objective 3

Several analyses will make use of a baseline behavioral risk score variable. This section describes how this variable will be constructed.

Let  $Y$  denote the primary efficacy endpoint indicator (i.e.,  $Y = 1$  if the endpoint was observed and  $Y = 0$  otherwise),  $W$  a vector of demographic and behavioral risk factors collected at baseline and specified in Table 3, and  $Z$  denote a vaccine indicator ( $Z = 0, 1$  denotes placebo, vaccine). For the  $i^{\text{th}}$  participant, we define the baseline behavioral risk score as a bivariate vector  $\left(\hat{P}(Y_i = 1 \mid Z_i = 0, W_i), \hat{P}(Y_i = 1 \mid Z_i = 1, W_i)\right)$ , where we use loss-based super-learning to estimate the best model for  $P(Y = 1 \mid Z = z, W) = E_0[Y \mid Z = z, W]$ ,  $z = 0, 1$ , where  $E_0$  denotes expectation under the true data generating distribution. This is a standard prediction problem. We estimate  $E_0(Y \mid Z = z, W)$  with a minimizer of the risk of a loss:  $\psi_0 = \arg \min_{\psi} P_0 L(\psi)$ , with  $Pf \equiv \int f(o) dP(o)$ . We select binary log-likelihood loss  $L(\psi)(O) = -\{Y \log \psi(W) + (1 - Y) \log(1 - \psi(W))\}$ , given its good performance for a rare event outcome, and we stratify by  $Z$  when fitting the risk minimization problem to ensure that we are estimating  $P(Y = 1 \mid Z, W)$  rather than  $P(Y = 1 \mid W)$ . To construct an optimal estimator among any given class of candidate estimators, we use loss-based super-learning. The oracle inequality for the cross-validation selector guarantees that the estimator is asymptotically at least as good as any candidate in the set of candidate estimators. We refer to [van der Laan, Polley, and Hubbard \(2007\)](#) and [Rose and van der Laan \(2011\)](#) for details.

Let  $\hat{\Psi}_j : \mathcal{M}_{NP} \rightarrow \Psi(\mathcal{M})$  be a candidate estimator that maps an empirical distribution of  $(O_1, \dots, O_n)$  (i.e., an element of the nonparametric model  $\mathcal{M}_{NP}$  of probability distributions) into the parameter space  $\Psi(\mathcal{M}) = \{\Psi(P) : P \in \mathcal{M}\}$ ,  $j = 1, \dots, J$ . This library of candidate estimators could include a variety of parametric model based estimators as well as a variety of machine learning algorithms, possibly coupled with different dimension-reduction strategies, and possibly indexed by a variety of tuning parameters.

Let  $B_n \in \{0, 1\}^n$  be a random split of the sample into a training sample  $\{i : B_n(i) = 0\}$  and validation sample  $\{i : B_n(i) = 1\}$ . For example, if we use  $V$ -fold cross-validation defined by a partitioning of the sample in  $V$  equal size groups, then  $B_n$  has  $V$  possible realizations, each occurring with probability  $1/V$ , and each split corresponds with setting the components of  $B_n$  in one of the  $V$ -folds equal to 1 and setting the other components equal to 0. Let  $P_{n, B_n}^0$  and  $P_{n, B_n}^1$  be the empirical distributions of the training and validation sample corresponding with split-vector  $B_n$ , respectively. The cross-validated risk of the  $j$ -th candidate estimator is then defined as  $E_{B_n} P_{n, B_n}^1 L(\hat{\Psi}_j(P_{n, B_n}^0))$ .

Define  $\hat{\Psi}_{\alpha} = \sum_{j=1}^J \alpha_j \hat{\Psi}_j$  as a weighted linear combination of the candidate estimators, where

Table 3: Baseline covariates used as input features  $W$  by the prediction/screening algorithms included in the construction of the superlearner model

Variable	Definition
site	Site Name
countryl	Country Name
aage	Age at Enrollment in Years (continuous)
bmibl	BMI at Enrollment (continuous)
arace	Race (Black, Colored/Mixed, Indian, Multiple, White)
syph	Syphilis Diagnosis at Enrollment (Positive, Negative, Not done/indeterminate)
ngonor	Gonorrhea Diagnosis at Enrollment (Positive, Negative, Not done/indeterminate)
ctrach	Chlamydia Trachomatis Diagnosis at Enrollment(Positive,Negative,Not done/indeterminate)
trich	Trichomonas Diagnosis at Enrollment (Positive, Negative, Not done/indeterminate)
agefsex	Age at First Sexual Intercourse in Years by the Time of Enrollment (continuous)
agesexp*	Age in Years of Oldest Sex Partner (continuous)
analsex*	Anal Sex (N = No, Y = Yes, Not Asked)
conduse	Condom Use by the Time of Enrollment (N = No, Y = Yes, Not Asked)
diagsti*	Diagnosed with STI (DK = Don't Know, N = No, Y = Yes)
exchsex*	Exchange Services for Sex (N = No, Y = Yes)
gendisch*	Genital Discharge (N = No, Y = Yes)
gensores*	Genital Sores or Ulcers (N = No, Y = Yes)
homearea	Type of Area Living In by the Time of Enrollment (Rural/Countryside, Urban/City/Town)
homemat	Main Materials of Home by the Time of Enrollment (Formal, Informal, Traditional, Other)
homserv	Building Has at Least Three Services by the Time of Enrollment (N = No, Y= Yes)
invag*	Insert Item (paper, cloth, etc.) Into Vagina to Make It More Dry for Sex (N = No, Y= Yes)
livbrths	How Many Babies Alive at Birth by the Time of Enrollment (continuous)
livwpart	Living with Main Sex Partner by the Time of Enrollment (N=No, Y=Yes, NA)
mainpart	Married or Have Main Sex Partner by the Time of Enrollment (N = No, Y= Yes)
nsexact*	Number of Sex Acts (number of times) (continuous)
nsexp*	Number of Sex Partners (number of people) (continuous)
othpart	Main Sex Partner Has Other Partners by the Time of Enrollment (N=No, Y=Yes, NA)
sexhipv*	Sex with HIV+ Partner (DK = Don't Know, N = No, Y = Yes)
usexalc*	Unprotected Sex with Alcohol Use (Never, 1-2 times, 3-5 times, 6 or more times)
usexhipv*	Unprotected Sex with HIV+ Partner (DK = Don't Know, N = No, Y = Yes)

\* The reference time-period is the previous month before enrollment

the weights  $\alpha_j$  are restricted to be non-negative and sum to 1. The cross-validation selector for the continuous family  $\{\hat{\Psi}_\alpha : \alpha\}$  of candidate estimators is defined as:

$$\alpha_n = \arg \min_{\alpha} E_{B_n} P_{n,B_n}^1 L(\hat{\Psi}_\alpha(P_{n,B_n}^0)),$$

and the super-learner is then defined as  $\hat{\Psi}(P_n) = \hat{\Psi}_{\alpha_n}(P_n)$ .

By the oracle inequality for the cross-validation selector we have that, if the expectation of the loss-based dissimilarity  $\min_{\alpha} E_{B_n} P_0 \{L(\hat{\Psi}_\alpha(P_{n,B_n}^0)) - L(\psi_0)\}$  between the oracle selected estimator and  $\psi_0$  converges to zero at a slower rate than  $1/n$ , then

$$\frac{E_0 E_{B_n} P_0 \{L(\hat{\Psi}_{\alpha_n}(P_{n,B_n}^0)) - L(\psi_0)\}}{E_0 \min_{\alpha} E_{B_n} P_0 \{L(\hat{\Psi}_\alpha(P_{n,B_n}^0)) - L(\psi_0)\}} \rightarrow 1, \text{ as } n \rightarrow \infty.$$

Table 4: Prediction and screening algorithms used by the superlearner for building the baseline behavioral risk score in the HVTN 705 trial

Learner	Screen*
SL.mean	all
SL.glm	all glmnet univar_logistic_pval highcor_random
SL.glm.interaction	glmnet univar_logistic_pval highcor_random
SL.glmnet	all
SL.gam	glmnet univar_logistic_pval highcor_random
SL.xgboost	all
SL.ranger.imp	all

\* Screen details:

all: includes all variables

glmnet: includes variables with non-zero coefficients in the standard implementation of SL.glmnet that optimizes the lasso tuning parameter via cross-validation

univar\_logistic\_pval: Wald test 2-sided p-value in a logistic regression model  $< 0.10$

highcor\_random: if pairs of quantitative variables with Spearman rank correlation  $> 0.90$ , select one of the variables at random

In other words, excluding the unrealistic situation in which one of our candidate estimators is a correctly specified parametric model, the super-learner is asymptotically equivalent with the oracle selected estimator.

In addition, we can evaluate the super-learner by its cross-validated risk, using a cross-validation scheme  $S_n$  (e.g., using  $V$ -fold cross-validation again as in the super-learner):

$$\text{CV-RISK} = E_{S_n} P_{n,S_n}^1 L(\hat{\Psi}(P_{n,S_n}^0)),$$

which involves rerunning the super-learner on learning samples  $\{i : S_n(i) = 0\}$  and evaluating it on test samples  $\{i : S_n(i) = 1\}$ , and averaging the performance across the different splits. When we do this for the trial, we will let  $S_n$  denote a random variable representing a mixture of 20 randomly selected 10-fold cross-validation schemes, so that the cross-validated risk can be evaluated by averaging the cross-validated risk from 20 different 10-fold cross-validation splits.

This represents an estimator of the true conditional risk

$$E_{S_n} R(\hat{\Psi}(P_{n,S_n}^0) \mid P_0) \equiv E_{S_n} P_0 L(\hat{\Psi}(P_{n,S_n}^0)),$$

and one can also construct a Wald-type 95% confidence interval for the latter true conditional risk parameter  $E_{S_n} R(\hat{\Psi}(P_{n,S_n}^0) \mid P_0)$  given by  $CV\text{-RISK} \pm 1.96\sigma_n/\sqrt{n}$ , where  $\sigma_n^2 = E_{S_n} P_{n,S_n}^1 \left\{ L(\hat{\Psi}(P_{n,S_n}^0)) - E_{S_n} P_{n,S_n}^1 L(\hat{\Psi}(P_{n,S_n}^0)) \right\}^2$ . The theory behind the asymptotic correctness of this data adaptive confidence interval is given in [Hubbard, Kherad-Pajouh, and van der Laan \(2016\)](#). We build the super-learner using the R package `SuperLearner` available on CRAN.

If the number of primary endpoints in each treatment group is  $> 30$ , we will use superlearner with 5-fold cross-validation, separately for the vaccine and placebo groups; otherwise leave-one-out cross-validation will be used. For the cross-validated superlearner, 5-fold cross-validation will be used for the outer cross-validation irrespective of the number of primary endpoints. These cross-validation rules align with those made for the baseline behavioral risk score analysis in Moderna’s COVE trial of the mRNA-1273 vaccine.

Table 4 shows the combinations of prediction and screening algorithms used by the super-learner. We will plot point and 95% CI estimates of the cross-validated area-under-the-ROC curves (AUCs) ([Hubbard, Kherad-Pajouh, and van der Laan, 2016](#)) for each individual learning approach as well as for discrete super-learner and super-learner, and, for each  $z = 0, 1$ , we will separately select the learner with the lowest cross-validated AUC for finalizing the risk scores  $(\hat{P}(Y_i = 1 \mid Z_i = 0, W_i), \hat{P}(Y_i = 1 \mid Z_i = 1, W_i))$ . For each  $z = 0, 1$ , we will report the cross-validated AUC of the best model as a summary of the quality of the risk score for the given study group.

## 9 Primary Analysis to Be Conducted at the End of Stage 1

The target Month 24 visit date for the last enrolled participant is May 25, 2021, with the upper allowable limit of the visit window on June 22, 2021. Unless the trial is stopped early, the target data cut date for the end-of-Stage-1 primary analysis will be May 28, 2021.

If the trial reaches the end of Stage 1, the primary analysis report will include the following SAP-specified analyses:

1. Primary objective 1 (parts of Section 8.1)
  - (a) Estimation of month 7–24 incidence rate, with 95% CI, by treatment arm in the PP cohort

- 
- (b) Estimation of month 7–24 cumulative incidence over time by treatment arm in the PP cohort
  - (c) Estimation of month 7–24 cumulative VE over time, with 95% pointwise and simultaneous CI, in the PP cohort, with the point estimate and 95% CI for the primary VE parameter reported at time point  $\tau$
  - (d) Two-sided Wald test of  $H_0$ : month 7–24 cumulative  $VE(\tau) = 0\%$  at  $\tau$  in the PP cohort
  - (e) Estimation of month 7–24 HR VE using the Cox model, with 95% CI, in the PP cohort
  - (f) Two-sided score test of  $H_0$ : month 7–24 HR  $VE = 0\%$  in the PP cohort
2. Secondary objective 2 (parts of Section 8.2.1)
    - (a) Repeat 1(a)–(f) except for the month 0–24 period and the MITT cohort
  3. Secondary objective 3 (parts of Section 8.2.1)
    - (a) Repeat 1(a)–(c) and (e) except for the month 13–24 period and the FIS cohort
    - (b) Repeat 1(a)–(c) and (e) except for the month 13–24 period and the cohort of MITT participants uninfected at month 13
  4. Additional efficacy analyses requested by Janssen
    - (a) Repeat 1(a)–(c) and (e) except for the cohort of MITT participants uninfected at month 7
    - (b) Repeat 1(a) except for the month 7–30 and 7–36 periods and the PP cohort
    - (c) Repeat 1(b)–(c) except for the month 7–36 period and the PP cohort
    - (d) Repeat 1(a) except for the month 0–30 and 0–36 periods and the MITT cohort
    - (e) Repeat 1(b)–(c) except for the month 0–36 period and the MITT cohort
    - (f) Repeat 1(a) except for the month 13–30 and 13–36 periods and the FIS cohort
    - (g) Repeat 1(b)–(c) except for the month 13–36 period and the FIS cohort
  5. Primary objective 2
    - (a) Maximum local reactogenicity by treatment assignment and the length of reactogenicity follow-up (3 days versus 7 days) (table and figure)
    - (b) Maximum systemic reactogenicity by treatment assignment and the length of reactogenicity follow-up (3 days versus 7 days) (table and figure)
    - (c) Adverse events by system organ class, severity, and treatment assignment (table)
    - (d) Adverse events by preferred term, severity, and treatment assignment (table)

- 
- (e) Adverse events related to study product by preferred term, severity, and treatment assignment (table)
  - (f) Listing of adverse events of special interest (AESIs), by preferred term and severity (listing)
  - (g) Serious adverse events (SAEs) reported to the global safety database ordered by treatment assignment, participant, and decreasing severity (listing)
  - (h) Adverse events leading to early participant withdrawal or early discontinuation of study administrations (listing)
6. Limited demographics and baseline disease characteristics, disposition and adherence tables, by treatment arm

Janssen will propose to the OG a list of recipients at Janssen of the analysis report. The OG's approval will be required before report distribution.

The analyses of vaccine efficacy through 30 months will define the final time point for analysis ( $\tau$ ) and the right-censoring process in the same way as described for the analyses of vaccine efficacy through 24 months, except now indexed off of the month 30 visit instead of the month 24 visit.

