4.4.4 Choice of control

The placebo control for Ad26.Mos4.HIV and Clade C gp140 is sodium chloride for injection, 0.9%.

4.4.5 HIV-1 incidence estimates from previous clinical trials among at-risk study populations in Southern Africa

The high rates of HIV acquisition amongst young women in Southern Africa highlight the need for biomedical interventions that are female controlled. Recent longitudinal studies evaluating various interventions indicate HIV incidence rates of between 4-11% and are summarized below:

Vaccine efficacy studies

• The HVTN 503 (Phambili) HIV vaccine study (2007), in which HIV-1 incidence among placebo recipients, 18-35 years of age was estimated at 3.7 per 100 person-years (5.86 for females and 1.93 for males) [33].

Topical and Systemic Pre-Exposure Prophylaxis Studies

- The FACTS 001 vaginal microbicide study (2011-2014), in which HIV-1 incidence was estimated at 4.0 per 100 person-years in women age 18-30 [34].
- The VOICE study of vaginal microbicide and systemic prophylactic antiretroviral drugs (2009-2013), in which overall HIV-1 incidence was 5.7% and incidence in the 3 placebo arms of the trial varied from 4.2 to 6.8 per 100 person-years, while the annual incidence in single women in South Africa aged 25 or younger was up to 10% [35].
- The MTN-020-ASPIRE dapivirine vaginal ring study (2012-2015), in which HIV-1 incidence was estimated at 4.5 per 100 person-years in female placebo recipients aged 18-45 in Malawi, South Africa, Uganda, and Zimbabwe [36].
- The RING study (IPM-027), a vaginal ring study (2012-2015), in which HIV-1 incidence was estimated at 6.1 per 100 person-years in female placebo recipients aged 18-45 [37].
- The Fem-PrEP, a study of PrEP effectiveness in HIV-negative women in Kenya, South Africa, and Tanzania (2009-2012), in which HIV-1 incidence was estimated at 5.0 per 100 person-years overall and ranged from 3.4–6 per 100 person-years in South African female placebo recipients aged 18-35 [38].

Based on a synthesis of the above references the estimated annual incidence rate of HIV-1 in Sub-Saharan women is 5.0% (total HIV acquisition events divided by total person years at risk). Under an assumed 90% PrEP efficacy during PrEP use, a conservative estimate of 4.2% annual HIV incidence can tolerate up to 15 out of 100 person years at risk during PrEP use.

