6.6 Assessment of PrEP use

The use of oral FTC/TDF as PrEP (either off-study or provided in the study) may impact study outcomes (e.g., by lowering HIV-1 incidence with a loss of study power). Dried blood spot (DBS) samples will be collected and stored for assessment of quantitative concentrations of intracellular tenofovir diphosphate (TFV-DP) (see Section 11.9). DBS samples will be collected and stored at pre-specified DBS sample collection days, which may vary by study site. The calendar-based selection of sample collection days will ensure representative sampling of participants across the entire visit schedule at all sites throughout the study. A detailed DBS sampling plan, specified in the statistical analysis plan, will be developed to prospectively monitor FTC/TDF use during the trial to inform the DSMB and to assess the potential impact of FTC/TDF use on endpoint accrual during the study. Prevalence of oral PrEP use will be reported both as the estimated percentage of person-years at-risk during highly adherent PrEP use (above the concentration of TFV-DP designated as consistent with daily dosing) and the estimated percentage of personyears at-risk during any detectable PrEP use (concentration of TFV-DP above the lower limit of detection for the DBS assay). PrEP use measures will be reported by arm to the DSMB in the closed session; in addition both the OG and the protocol team leadership will see pooled estimates of FTC/TDF use.

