6.9.5.2 Secondary vaccine efficacy analyses: HIV-1 acquisition

Vaccine efficacy for MITT and FIS

The analyses above will be repeated for the MITT population and the FIS.

Durability of vaccine efficacy

Vaccine efficacy over all available follow-up times will be assessed using the method of Parzen, Wei, and Ying described above, as well as with nonparametric hazard ratio estimation [50] and with Cox proportional hazards modeling with time-dependent covariates. If the analysis suggests time-invariant vaccine efficacy, then the Cox model will be used to estimate proportional-hazards VE and to test for VE different from zero accounting for all available follow-up time. The SAP will provide details of these analyses.

Vaccine efficacy in the absence of PrEP

The primary analysis will be repeated, where only MITT or PP infections in participants who were not using prophylactic ARVs at the time of HIV-1 diagnosis or first evidence of infection will be included in the analysis. Plasma drug levels will be used to determine eligibility for this analysis. A participant is eligible if the plasma drug levels are undetectable at the diagnosis visit and at the visit with earliest evidence of HIV-1 infection (if different from the diagnosis visit). Since the ARVs are only detectable in plasma through roughly 14 days [51] and some participants may have become infected before the 14-day window, with this approach we are not assured that all those included in the analysis were not using prophylactic ARVs at the time of infection. Therefore, an additional analysis will address this issue by also excluding participants from the HIV-1 acquisition analysis if they self-reported drug use in the last 30 days at either the diagnosis visit or the last visit prior to diagnosis. This additional analysis will evaluate uninfected participants without accounting for data on their plasma drug levels.

Vaccine efficacy by subgroups

The primary analysis may be repeated for different subgroups. Wald tests for interaction in the context of Cox proportional hazards models will be used to test for evidence of differential vaccine efficacy by subgroup.

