11.9 ARV detection

ARV testing will be performed using a test that measures the amount of tenofovir-diphosphate (a metabolite of tenofovir) in red blood cells. This test utilizes a dried blood spot as the sample source and analyzes for tenofovir diphosphate by liquid chromatography and tandem mass-spectroscopy, as previously described [54,55]. Stored serum and plasma (see Appendix F) will allow additional assessment of PrEP use if warranted.

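### SAP 8.4 and protocol 6.9.5.2 use different assays to decide eligibility for the PrEP-free efficacy analysis, and the SAP has no rule for endpoints without a blood spot

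*SAP*

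**What the plan says.** Protocol 6.9.5.2, in the paragraph on efficacy in the absence of PrEP, states: "Plasma drug levels will be used to determine eligibility for this analysis". Drug must be undetectable at the diagnosis visit and, if it is a different visit, at the one with the earliest evidence of infection.

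SAP 8.4 describes the same analysis. It includes "only MITT infection endpoints with no evidence of PrEP use at the time of HIV-1 diagnosis", then bases eligibility on intracellular tenofovir with a pointer to SAP 8.3. That section is a single sentence pointing to SAP 10.2, which describes tenofovir diphosphate measured in DBS. The operative rule is: "A participant is eligible if the TFV concentration is below the lower limit of detection as defined above at the diagnosis visit", and the same at the earliest-evidence visit. The limitation that follows is still about plasma: "Since the ARVs are only detectable in plasma for roughly 14 days".

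The protocol is not uniform either. Of the ARV test, section 11.9 says: "This test utilizes a dried blood spot as the sample source". It adds that stored serum and plasma "will allow additional assessment of PrEP use if warranted". Appendix E, footnote 9, permits EDTA plasma for ARV detection, and footnote 10 leaves the ARV testing plan open.

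On timing, protocol 6.6 says: "DBS samples will be collected and stored at pre-specified DBS sample collection days, which may vary by study site". SAP 10.2.1 adopts schedule S2, the business days nearest the 1st and 15th of each month. SAP 10.2 allows the frequency to be raised.

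**The concern.** The two documents give different eligibility rules for one analysis, and the SAP's version is only partly converted: the criterion changed matrix and the justification did not. The SAP's modification history does not mention the difference.

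The change matters because the two samples differ in availability. EDTA blood is drawn at every scheduled HIV-diagnostic visit. Spots are drawn on calendar days chosen to estimate PrEP prevalence in the cohort, so many endpoints may have none at the visit that counts. SAP 8.4 does not say what happens then. One sentence admits endpoints with no evidence of PrEP use, which a missing spot satisfies. A later one requires a value below a limit, which a missing spot cannot satisfy. The choice between them would be left until the data are in hand.

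**Working it through.** **1. Detection limit.** Nothing above SAP 8.4 defines one. Protocol 6.6 uses the DBS assay's lower limit of detection, without a value. SAP 10.2, which comes later, uses the lower limit of quantitation, also without a value. The only number, 1,000 fmol/punch, defines effective use and not detection.

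**2. Pool of endpoints.** SAP 10.3.2.2 gives person-years T* = N(1 - exp(-2(p + d)))/(p + d), with N = 2600, dropout d = 0.10 and pooled rate p = 0.0330. This returns 4565.85, as stated. Infections: 0.0330 x 4565.85 = 150.7 (150.8 with unrounded p), against a median of 150 in protocol Table 6-5. With p = 0.042 (VE 0%) the result is 190.1, against 190. Both reproduce.

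**3. Spot coverage.** S2 from 1 November 2017 (the start date in the SAP's simulation) to 30 June 2021 covers 44 months, so 88 collection days among 956 weekdays, public holidays ignored. If a visit is equally likely to fall on any weekday, coverage is 88/956 = 9.2%.
- Diagnosis visit only: 0.0921 x 150 = 13.8, about 14 endpoints.
- This is an upper bound under S2, because a different earliest-evidence visit also needs a spot. If that visit always differed and fell independently: 150 x 0.0921² = 1.3.
- With schedule S3: 132/956 = 13.8%, about 21 endpoints. With S2 doubled: 2 x 0.0921 x 150 = 27.6, about 28.

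**4. A measured undetectable spot is required.** Take VE(0-24) = 43% from SAP 10.3 (RR 0.57) and split events 1 : 0.57. SE(log RR) = sqrt(1/placebo events + 1/vaccine events).
- 14 events: 8.92 and 5.08; SE = 0.556; RR limits exp(-0.562 ± 1.96 x 0.556) = 0.19 to 1.69; VE from -69% to 81%.
- 150 events: 95.5 and 54.5; SE = 0.170; VE from 20% to 59%.

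**5. A missing spot counts as no evidence of PrEP.** Protocol 4.4.5 works "Under an assumed 90% PrEP efficacy during PrEP use". SAP 10.2.1 simulates 10% and 20% of person-time on PrEP. If a fraction u of person-time is on effective PrEP, equally in both arms, and users have the same background risk, the share of endpoints arising on PrEP is 0.1u/(1 - 0.9u).
- u = 0.10: 1.10%, or 1.6 of 150. u = 0.20: 2.44%, or 3.7 of 150.
- Removed by a diagnosis-visit spot (x 0.0921): 0.15 to 0.34 on average. The chance that none is removed is (1 - 0.0921 x share)^150 = 86% to 71%.
- If every endpoint had a second, separate visit, coverage would be 1 - (1 - 0.0921)² = 17.6%, which less than doubles these averages.

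Detectable but ineffective use would add an unknown number of removals.

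**6. Plasma.** Appendix E schedules an EDTA tube for viral isolation at all nine post-enrolment HIV-diagnostic visits through Month 24.

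**The case against.** The strongest reply is that S2 was chosen for the precision of a prevalence estimate, and neither document says it limits testing of infected participants. Appendix E sends DBS collection details to the Study Specific Procedures, which are not among the documents, and SAP 10.2 allows more frequent collection. This stands. A reader might infer that the analysis will rest on 14 endpoints, but the documents do not support that. The figure is conditional, and under its conditions it is a ceiling.

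Protocol 11.9 names DBS as the ARV test, so DBS is not foreign to the protocol. That also stands, but 6.9.5.2 is the specific rule for this analysis, and it says plasma.

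The missing limit is largely a stale cross-reference plus two terms for the assay threshold. That is fair, and it is the smallest part of the point.

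Two further inferences should be resisted. The heading of SAP 8.4 does not show that a secondary analysis was demoted to exploratory: exploratory objective 2 in SAP 2.3 is the vaginal microbiome, so the heading appears mislabelled. Nor should calendar-day sampling be read as biasing the estimate. If visit days are unrelated to PrEP use, the loss is of precision.

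Finally, SAP 8.4 opens with analyses conditional on substantial PrEP use, and this one may share that condition and never be run. That limits the importance of the point without resolving the conflict.

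**Conclusion.** The contradiction holds on the text alone: plasma in protocol 6.9.5.2, the DBS assay in SAP 8.4 with a plasma rationale, a reference to a limit not defined above, and no rule for endpoints without a spot. No sampling frequency cures the conflict of matrix.

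Its size is conditional on S2 not being intensified, no diagnosis-triggered spot in the Study Specific Procedures, and visits spread evenly over weekdays. At most about 14 of 150 MITT endpoints then have a spot. The analysis is either too imprecise to interpret or nearly the same as the unfiltered MITT analysis. In the second case the shift in VE would be small, since few endpoints are expected on effective PrEP. The harm is a result labelled PrEP-free that has scarcely been filtered.

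A reader might infer a threat to the trial's main conclusion. There is none: the primary VE(7-24) analysis, the stopping rules and the Stage 2 decision do not use this filter. The point deserves correction, with moderate confidence in its practical size.

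**What to change.** - Amend SAP 8.4 so that eligibility is undetectable drug in stored EDTA plasma at the diagnosis visit and at the earliest-evidence visit, as in protocol 6.9.5.2. Use DBS results, where they exist, as supportive evidence.
- Correct the cross-reference and use one detection-limit term for the chosen assay.
- State that an endpoint with no usable sample is not counted as PrEP-free, and add a sensitivity analysis that includes such endpoints.
- Keep the additional analysis based on self-reported ARV use.
- Make protocol 11.9 name the same matrix for this analysis.

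The cost is wording in two documents and at most two plasma assays per infected participant: up to about 300 (2 x 150) at the design alternative, or 380 (2 x 190) at VE 0%. No new blood draw is needed. There are two drawbacks. The plasma is shared with viral sequencing. With a detection window of about 14 days and visits roughly three months apart, an undetectable result is weak evidence about PrEP use at the time of infection, which is why the self-report analysis should stay.
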